**Optimizing Cognitive, Environmental, and
Neuromotor Stimulation in Traumatic Brain Injury**

NCT04073225

1/8/2024

Date: January 8, 2024

Principal Investigator: [name]

Application Number: IRB00218229

JHM IRB - eForm A – Protocol

- Use the section headings to write the JHM IRB eForm A, inserting the appropriate material in each. If a section is not applicable, leave heading in and insert N/A.
- When submitting JHM IRB eForm A (new or revised), enter the date submitted to the field at the top of JHM IRB eForm A.

1. Abstract

- a. Provide no more than a one page research abstract briefly stating the problem, the research hypothesis, and the importance of the research.

Patients with a history of traumatic brain injury (TBI) are at elevated risk for Alzheimer's disease and related dementias (ADRD). Improvements in TBI treatment may mitigate this risk. The treatment of TBI, especially for those with chronic neuropsychiatric sequelae, is moving toward multi-modal approaches that include non-pharmacological interventions such as exercise and cognitive enrichment. Complex motor activities, which combine physical and cognitive demands, have been shown to have well established neurocognitive benefits. However, there are a lack of cognitive enhancing interventions that utilize these complex motor activities. Many adults with history of TBI face significant barriers to engaging in physical activity which limit their ability to participate in many neurocognitive interventions. This study seeks to address the need for novel TBI interventions optimized for adults with history of TBI by determining the effectiveness of an immersive computer game designed to integrating complex cognitive-motor processes. During this proposed 12-month study involving patients with history of TBI (n=66) we will examine cognition, independent function, mood and ADRD-related brain biomarkers after 12 weeks of a randomized intervention, as well as 9 months post-intervention to assess for durability of any benefits. We hypothesize that complex motor activities will improve cognitive health in adults with a history of TBI and that promising results would have implications for early intervention for those at risk for mild cognitive impairment and ADRD.

2. Objectives (include all primary and secondary objectives)

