- 1) Primary Objective: To determine the efficacy of a complex cognitive-motor game, Bandit (intervention), on cognition, lifestyle, independent activities of daily living (IADL), activities of daily living (ADL), psychological and physical well-being, sleep, physical activities, and social networks in patients with past TBI in comparison to a Successful Aging Program (active control).
- 2) Objective 2: To examine mechanistic brain biomarkers of ADRD prior to and following 3 months of exposure.
- 3) Objective 3: To assess durability of any observed cognitive, lifestyle, and IADL benefits 9-months post-exposure.

3. Background (briefly describe pre-clinical and clinical data, current experience with procedures, drug or device, and any other relevant information to justify the research)

Studies have shown that those with past TBI are at elevated risk for ADRD. The brain networks most impacted post-TBI, the prefrontal cortex (PFC) and the hippocampus, are also related to the pathological processes involved in ADRD. The PFC network helps with executive processes involved in the initiation, planning, coordination, and sequencing of actions toward a goal. Executive functioning is the cognitive domain found to have the strongest impact on functional outcomes after TBI. Research has also shown that loss of brain volume in the early stages of Alzheimer's disease is greater in the PFC than in other areas of the brain. The hippocampus is functionally linked to spatial navigation and memory through the consolidation of information learned as one physically moves from location to location. The hippocampus declines most precipitously with age and is further implicated in risk for dementia. These findings suggest that improving the treatment of TBI may be an important strategy for the early intervention of ADRD.

[figure not shown]
A growing body of research suggests that non-pharmacological interventions have the potential to provide powerful treatment options for those with chronic cognitive, mental and physical sequelae after TBI. Evidence shows that even moderate physical activity such as low-intensity walking improves neurocognitive health. Cognitive enrichment from various daily activities has also been found to have beneficial effects on cognition and risk for neurodegenerative disorders.

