- Evaluations will consist of a detailed review of the consent form, demographic survey, physiological measures (e.g., height, weight, blood pressure, pulse), physical function measures, cognitive tests, and surveys to evaluate knowledge, attitudes, and behaviors around technology use, well-being, sleep, lifestyle activities, physical activities, social networks, depression, health status, independent activities of daily living, and activities of daily living. All measures that can be completed remotely prior to visit, with the research assistant outside of the room, or with the research assistant greater than 6 feet from the patient will be.
- Participants will be asked to wear an Apple Watch paired with an iPhone and an Actigraph for 2 weeks prior to starting the intervention. Participants will be given hands-on education on the use of the these devices at baseline and provided on-call support while wearing them. For those who have an iPhone, we will offer to provide the iPhone or if they prefer, we can download the secure physical activity monitoring research app at no cost. This app does not collect personally identifiable information and can be easily removed from their iPhone.

- The pre-intervention MRI scan will be scheduled at this visit and completed prior to intervention start.

Intervention Visits (in-person)

- After 2 weeks of using the Apple Watch paired with an iPhone and Actigraph to measure baseline activity levels, participants will have their first intervention visit.
- The day prior to each intervention visit, research staff will call the participants to complete the COVID-19 clinical screening questions. If participants screen positive, the visit will be canceled.
- All intervention visits will occur at Hampton House Room 398, the Bayview clinic, or Howard County General clinic. Parking will be vouchered for participants, if applicable.
- Universal masking will be used for participants and research staff. Research staff will use a face shield whenever a distance of 6 feet cannot be maintained. Cleaning protocols will occur as per CDC guidelines and only one research participant will be in the room on a given day (only one per cleaning).
- During the first intervention visit:

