It is important to include a control in this study because the video game being evaluated is designed to be multi-modal through integrated, complex cognitive and physical activity. To better isolate the impact of this multi-modal approach relative to physical exercise alone, it is important to compare any benefits of Bandit play to the benefits of the Successful Aging Program with an integrated placebo exercise component. .

In order to minimize bias in the assessment of outcomes of the two treatment arms, the study greatly benefits from blinding the research team as much as possible. Given the nature of the study, the participants will not be blinded.

d. Justification of why participants will not receive routine care or will have current therapy stopped.

N/A. No adjustments will be made to the standard of care in regard to medication or therapy during the study.

e. Justification for inclusion of a placebo or non-treatment group.

The Successful Aging Program will be used as the active control group for this study. This program is an active health education intervention (approximately 60 minutes long) based on staff attention both through lectures from the Prevention Research Center 10 Keys to Successful Aging materials on a variety of topics related to older adults. A short instructor led program (5-10 minutes) of upper extremity stretching exercises (a “placebo exercise”) will be performed during each class to help foster adherence without directly affecting the study outcomes. In addition to the 60 minute in-person instructor led group, participants will be encouraged to spend two hours a week on take-home activities from the 10-key participant workbook and/or work on their personal health goals. We feel this group is necessary to account for the treatment effect caused by frequent visits and exercise alone.

f. Definition of treatment failure or participant removal criteria.

If the participant no longer wishes to be enrolled in the study, they will be excused with no consequence to their ongoing treatment and physician care. Subjects who become suicidal or develop problems that require aggressive treatment during the course of the study will be withdrawn, and followed at their established clinic, if appropriate care can be provided on an outpatient basis. If outpatient care is not appropriate, the clinical PI ([name]) will be responsible for admitting subjects.

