An interim-analysis will be performed on the primary outcomes when 1/3rd (n=22) of patients have been randomized and have completed the 12 weeks of study intervention and post-intervention follow-up visit. The interim-analysis will be completed by a statistician blinded from the treatment arm. The statistician will report to the independent data safety monitoring board (DSMB). The DSMB will have unblinded access to all data and will discuss the results of the interim-analysis. The DSMB will decide on continuation of the trial. If the DSMB feels a case of futility is present, they will discuss with the investigators, and IRB if necessary, to decide on continuation of the trial.

b. Primary outcome variable.

Primary Objective, Primary Outcomes:

Objective #1, Primary Outcomes

Cognitive outcomes: We will assess executive function, psychomotor and perceptual speed, and verbal learning and memory. Four tests will be administered: the Trail Making Test (TMT), the Stroop Test, the Pattern Comparison Test, and the Rey Auditory Verbal Learning Test (RAVLT). The TMT is comprised of two timed parts, A and B, that requires participants to connect numbers in an ascending sequence (Part A measures psychomotor speed) and in ascending alphanumeric sequence, numbers and letters (Part B measure executive function). The Stroop test requires one to name as quickly and accurately as possible the color of ink that color-words are presented in (e.g., “red” presented in blue ink) and assesses one’s ability to inhibit a well-practiced response (word reading) in favor of a less-practiced response (inhibitory executive function). Perceptual speed will be assessed using the Pattern Comparison Test, requiring one to compare as many pairs of 32 line drawings as possible in 30 seconds and to determine whether members of each pair are similar or different. Verbal learning and memory will be assessed with the RAVLT which is comprised of 3 presentations and 3 recalls of a 15-word list as well as a 20-minute delayed recall of the word list.

Physical Mobility outcomes: Performance-based measures of mobility will be performed using the Short Physical Performance Battery (SPPB). Measures include:

- Walking speed, both usual and rapid pace, over a 4 meter course.
- Ability to rise from low chair without using arms.
- Balance: Functional reach and static stands: side-by-side, semi-tandem and tandem.

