the number of patients with TBI seen at the clinical sites and given what is feasible for us to complete the study visits in the time provided through Department of Defense (DoD) grant funding.

Data Analytic Plan:

- Definition and selection of dataset: Using an Intention-to-treat (ITT) design, all randomized participants will be included and followed up as available. The per-protocol (PP) population will include all participants in the ITT population who are compliant with study treatment as defined by >70% session exposure. Baseline demographic and clinical characteristics, including time since TBI, severity, medical comorbidity, and post-concussive symptoms will be included as covariates in the ITT dataset. Pre-post intervention benefits will be assessed using both ITT and PP datasets.
- Basic exploratory analyses will first be conducted, including checking of distributional assumptions, assessment of relationships among covariates, and missing-value multiple imputations.
- Continuous variables will be described by using mean, standard deviation, median, minimum and maximum, and 95% confidence interval for parameter estimation. Graphical display (spaghetti plots) of the outcome scores will also be generated for the 4 visits (baseline, 3 months, 9 months and 12 months) by group. Category and count variables will be described using frequency or proportions.
- Analyses will be conducted using STATA 11.2 (StataCorp, Texas, 2009) or R 2.13.2(2011). All statistical tests will be judged for significance based upon a two-sided p-value of less than 0.05.

e. Early stopping rules.

- If it is deemed that the participant requires a higher level of care (inpatient hospitalization), they will be removed from the study.

8. Risks

a. Medical risks, listing all procedures, their major and minor risks and expected frequency.

We do not expect any anticipated adverse outcomes for the study participants. The risk is minimal and therefore no harm is expected to be done to participants.

Risk associated with study involvement: As this study includes research as part of standard clinical care, there is a minor risk of unintentional release of protected health information. Risks in regard to assessments are limited to boredom, fatigue, and frustration. Additionally, given the time spent outside of their homes, participants risk exposure to COVID-19.

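### Section 7d describes efficacy only as pre-post benefit and does not commit to adjusting for the outcome's own baseline score, a modest gain in precision from data already collected

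*Combined protocol and SAP*

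**What the plan says.** Section 7d, Data Analytic Plan, defines the ITT and per-protocol (PP) sets and then says "Pre-post intervention benefits will be assessed using both ITT and PP datasets". It names no model, arm term, contrast or timepoint. The rest of that plan covers exploratory checks, multiple imputation, descriptive summaries, plots, software and a two-sided 0.05 threshold.

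On covariates, 7d says "Baseline demographic and clinical characteristics, including time since TBI, severity, medical comorbidity, and post-concussive symptoms will be included as covariates". The four named items describe the injury and the patient. None is the baseline value of an outcome, though the word *including* leaves the list open.

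Other sections supply part of what 7d omits:

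- **Contrast.** The primary objective (Section 2) is set "in patients with past TBI in comparison to a Successful Aging Program (active control". Section 4c explains that the control is there to "compare any benefits of Bandit play to the benefits of the Successful Aging Program".
- **Timepoint.** The Abstract examines outcomes "after 12 weeks of a randomized intervention, as well as 9 months post-intervention to assess for durability of any benefits". The interim analysis (Section 7a) uses patients who "have completed the 12 weeks of study intervention and post-intervention follow-up visit".
- **Baseline data.** Under Section 4a, the pre-intervention evaluation includes cognitive tests, physical function measures and surveys, and the post-intervention visit repeats them. For MRI, "The pre-intervention MRI scan will be scheduled at this visit and completed prior to intervention start", and a second scan follows the intervention. Objective 2 is "To examine mechanistic brain biomarkers of ADRD prior to and following 3 months of exposure".

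**The concern.** Even if a between-arm comparison at 12 weeks is taken as read, the efficacy sentence does not say how the baseline score enters it. A comparison of change scores and a baseline-adjusted comparison (ANCOVA) both fit the wording. They give different standard errors and p-values from the same data.

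Two things are at stake. The first is precision. With similar variance at both visits, a change score over-corrects for baseline whenever the correlation is below 1, whereas ANCOVA estimates the right amount of correction. Section 7d ties the sample size partly to what clinic volume and grant funding allow, so precision from measures already planned is worth having. The second is pre-specification. There are many primary outcomes and no named test, so the choice would otherwise be made with the data in hand.

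**Working it through.** **Inputs from the documents (Section 7d).** Total evaluable sample 66; alpha 0.05, two-sided; effect sizes 0.91 and 0.75 with SD 0.33, so the difference is 0.91 − 0.75 = 0.16.

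**Assumptions, not in the documents.** 1:1 allocation (33 per arm); equal variance at both visits; baseline-to-follow-up correlation r from 0.5 to 0.9; 0.33 as the SD of a score at one visit; no other covariates in the closed-form figures.

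**The plan's own figure.** No power is stated, so 66 cannot be checked directly. At 80% power, two-sided, n per arm = 2 × (1.96 + 0.84)² × (0.33/0.16)² ≈ 67, or 134 in total. With 33 per arm, a two-sample t-test on scores at one visit has 49% power. Other readings of the inputs come closer to 66, but none is stated. I take 66 only as the fixed sample size; its derivation is a separate matter.

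**Variance factors, relative to 0.33².**

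- Change score: 2(1 − r), with 64 degrees of freedom.
- ANCOVA: (1 − r²) × 63/62, with 63 degrees of freedom. The factor (N − 3)/(N − 4) = 63/62 ≈ 1.016 is the price of estimating the baseline slope, about 1.6% in variance.
- Ratio of ANCOVA to change score: (1 + r)/2 × 63/62. The equivalent sample is 66 divided by this ratio. At r = 0.5 that is 66/(0.75 × 1.016) ≈ 87.

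Power is from the noncentral t with standardized difference 0.16/0.33 = 0.485 divided by the square root of the variance factor.

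| r | Change-score variance | ANCOVA variance | Change-score power | ANCOVA power | Gain (points) | 66 patients do the work of |
|---|---|---|---|---|---|---|
| 0.5 | 1.00 | 0.762 | 49% | 60% | 11 | 87 |
| 0.6 | 0.80 | 0.650 | 58% | 67% | 9 | 81 |
| 0.7 | 0.60 | 0.518 | 71% | 77% | 6 | 76 |
| 0.8 | 0.40 | 0.366 | 87% | 89% | 3 | 72 |
| 0.9 | 0.20 | 0.193 | 99% | 99% | under 1 | 68 |

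**Other readings of the inputs.**

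- *0.33 as the SD of change.* Change-score power is 49% at every r. ANCOVA variance relative to 0.33² is (1 + r)/2 × 63/62, which gives 60, 58, 55, 53 and 51%. The gain is about 11, 8, 6, 4 and 1 points.
- *0.91 and 0.75 already standardized.* The difference is 0.16 SD. At r = 0.5 to 0.8, change-score power is 10, 11, 13 and 17%, and ANCOVA power is 11, 12, 14 and 18%. The gain is at most about 2 points.

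**With the planned covariates already in the model.** In a simulation of 10,000 trials per cell, four covariates explained an assumed 0 to 20% of variance. At r = 0.5, 0.6, 0.7 and 0.8, change-score power was 47, 55, 68 and 84–85%. Adding the baseline score gave 59–61, 64–68, 75–76 and 87–88%. The planned covariates therefore do not replace the baseline score. Type I error of the baseline-adjusted model was 0.050 and 0.049 in the two settings tried.

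**The case against.** The strongest reply is that little is missing. The comparison with the control is in the primary objective and in the control rationale, 7d analyses all randomized participants, and the sample-size paragraph starts from two arms. The covariate list is open and can take a baseline score. All of this stands, which is why stating the contrast and timepoint is only a clarification.

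The gain is also modest and unanchored. It shrinks to under 1 point at r = 0.9 and is at most about 2 points on the standardized reading. It rests on one Stroop metric from a cited pilot. Nor is the covariate entirely free, since it takes one degree of freedom. This stands too, and the table charges for it. What remains is that nothing in the plan commits to the better analysis.

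A reader might infer more than the documents support:

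- **That each arm will be tested separately against its own baseline, with Bandit declared effective if only its arm is significant.** The objective and Section 4c point to a comparison between arms, so error rates for separate within-arm tests are no evidence against this plan.
- **That only follow-up scores will be compared, which would make the gain look much larger at high r.** Pre-post wording naturally uses the pre-intervention score, so the change score is the fair comparator.

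**Conclusion.** The point holds as a should-fix on specification and precision. Section 7d neither states how the baseline score is used nor names it among the covariates, although it is collected. Against a change-score analysis, baseline adjustment adds about 11, 9, 6, 3 and under 1 points of power at r = 0.5 to 0.9, given 33 per arm, equal variances, a difference of 0.16 and a single-time SD of 0.33. It adds at most about 2 points if the effect sizes are already standardized. Confidence is high on the omission and low on the size of the gain, because the documents give neither r nor the meaning of the SD. The pre-specification benefit does not depend on either.

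The documents do not support saying that the trial lacks a between-arm comparison or that baseline scores are ruled out.

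**What to change.** In Section 7d, replace the efficacy sentence with:

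> For each primary outcome of Objectives 1 and 2, the analysis is the between-arm difference (Bandit minus Successful Aging Program) at the 3-month post-intervention evaluation. It comes from a regression model suited to the outcome (ANCOVA, or an equivalent baseline-adjusted mixed model, for continuous outcomes) with arm, the baseline value of that outcome and the planned baseline covariates. It is fitted in the ITT dataset and repeated in the PP dataset. The 12-month evaluation is analysed in the same way for Objective 3. Scalar secondary outcomes measured at both visits and able to change with treatment are analysed in the same way.

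The last sentence is limited on purpose. The Early Enrichment questionnaire concerns activities before adolescence and cannot respond to treatment, and group independent component analysis of resting-state fMRI does not give a single score per patient.

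A separate, minor correction: the plot description in 7d lists four visits, including both 9 and 12 months. Section 4a makes the evaluation 9 months post-intervention the third one, at month 12. List baseline, 3 months and 12 months. This affects descriptive plots only.

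The cost is wording, plus one degree of freedom per model (about 1.6% in variance at 66 patients). No patient, visit or measure is added.

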Grip Strength will be measured with a dynamometer and captures upper limb muscular strength.

Self-reported whole-body physical and mental tiredness will be measured using the Pittsburgh Fatigability Scale.

IADL outcomes: Self-reported measures of physical function performing Independent Activities of Daily Living (IADLs)

ADLs outcomes: Self-reported measure of physical function performing Activities of Daily Living (ADLs).

Objective #2, Primary Outcome

Brain MRI Volumetrics: We will obtain 3-T volumetric data on a research-dedicated Philips 3 Tesla (T) scanners using previously described methods. We will obtain various volumetric measures, including:

hippocampus, amygdala, mediotemporal cortex, orbitofrontal cortex, striatum, total gray matter, and total white matter using standard software packages including Freesurfer, SPM and MRICloud.

Objective #3, Primary Outcome:

Same as primary objective, primary outcome

- c. Secondary outcome variables.

Primary Objective, Secondary Outcomes:

Activity outcomes: The following physical activity will be assessed with an Apple Watch paired with iPhone and an Actigraph:

- Summary metrics include: total counts/day (amount); total minutes of activity/day (duration); total bouts of activity/day (duration); levels of activity intensity (sedentary to vigorous) and accumulated time within each activity level.
- We will additionally include a novel, validated metrics, including active (non-rest) time and variability, intensity of movement and daily time- stamped, or diurnal, patterns of low, moderate, and vigorous activities.
- The following data on heart rate will be assessed using the heart rate sensor on the Apple Watch: - Summary metrics include: BPM –beats per minute; resting HR (non-intervention); on-intervention HR; HR variability (Standard deviation of all HR intervals, Standard deviation of the averages of HR intervals in activity bouts.

Neuropsychiatric Symptoms: The following data will be collected to assess for neuropsychiatric symptoms:

- The Patient Health Questionnaire-9 (PHQ-9) depression scale will be used for depression screening measures.
- The Neuropsychiatric Inventory–Questionnaire (NPI-Q) will be used to provide a brief assessment of neuropsychiatric symptomatology.

Lifestyle and Physical Activity: The following questionnaires will be given to assess lifestyle and physical activity.

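### Nine primary clinical instruments, each tested at p<0.05, with no lead endpoint, adjustment or success rule

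*Combined protocol and SAP*

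**What the plan says.** Section 2 gives the primary objective in terms that begin "To determine the efficacy of a complex cognitive-motor game, Bandit (intervention", with the Successful Aging Program as active control.

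Section 7b then lists the Objective 1 primary outcomes, in the plural:

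- Cognition: "Four tests will be administered: the Trail Making Test (TMT), the Stroop Test, the Pattern Comparison Test", with the Rey Auditory Verbal Learning Test (RAVLT) as the fourth.
- Mobility: "Performance-based measures of mobility will be performed using the Short Physical Performance Battery (SPPB". Walking speed at two paces, chair rise, functional reach and static stands are listed as its measures. Grip strength follows.
- Fatigue: "Self-reported whole-body physical and mental tiredness will be measured using the Pittsburgh Fatigability Scale".
- Self-reported IADL and self-reported ADL.

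That makes nine instruments. Objective 2 has its own primary outcome, an open list of brain volumes that includes "hippocampus, amygdala, mediotemporal cortex, orbitofrontal cortex, striatum, total gray matter, and total white matter". For Objective 3, the month-12 durability assessment, the entry is "Same as primary objective, primary outcome".

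On inference, section 7d says only: "All statistical tests will be judged for significance based upon a two-sided p-value of less than 0.05". It states an intention-to-treat design, but it assesses benefit in both the ITT and per-protocol sets and does not say that the second is supportive. The sample size in section 7d refers to the Stroop test alone. Section 7a also uses the plural: "An interim-analysis will be performed on the primary outcomes when 1/3rd (n=22) of patients have been randomized".

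**The concern.** A trial meant to determine efficacy needs a stated rule for turning its primary results into a yes or no. This plan has nine primary results, each with its own 5% test and no rule for combining them. One favourable result out of nine could be reported as efficacy, and the plan gives no agreed ground for discounting it. A mixed outcome, such as better grip strength with unchanged cognition, has no agreed reading either. The choice cannot be made credibly once comparative data have been seen.

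**Working it through.** **1. The plan's own figures.** The documents give no familywise error rate. The only related number is a total of 66 at alpha 0.05, with power and allocation unstated, taken from Stroop values of 0.91 and 0.75 with SD 0.33. Read as arm means, the standardised difference is (0.91 − 0.75)/0.33 = 0.16/0.33 = 0.485. An unadjusted 1:1 two-sample comparison, one- or two-sided at 0.05 with 80 to 90% power, needs 106 to 180 in total, so 66 is not reproduced this way. That is a separate matter. It is used below only to price the fix.

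**2. Number of tests.** TMT, Stroop, Pattern Comparison and RAVLT (4), SPPB (5), grip (6), Pittsburgh Fatigability Scale (7), IADL (8), ADL (9).

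**3. Assumptions not in the documents.** No true effect on any outcome; one between-arm test per instrument at month 3; any one significant result counts as success; equal pairwise correlation ρ.

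**4. Formula.** Two-sided 0.05 leaves 0.025 in the direction favouring the game.

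- Independent outcomes: 1 − 0.975^9 = 0.204. Either direction: 1 − 0.95^9 = 0.370.
- Correlated outcomes, favouring the game: 1 − ∫ Φ((1.96 − √ρ·x)/√(1−ρ))^9 φ(x) dx, with the matching two-sided form for either direction.

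| Nine tests | ρ = 0 | 0.3 | 0.5 | 0.8 | One test |
|---|---|---|---|---|---|
| Favouring the game | 20.4% | 16.5% | 13.5% | 8.3% | 2.5% |
| Either direction | 37.0% | 32.6% | 26.9% | 16.6% | 5% |

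Simulated two-sample t-tests with 33 per arm (40,000 trials) gave 20.7% at ρ = 0 and 13.3% at ρ = 0.5, so the normal approximation is adequate.

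**5. Other counts.**

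- *Sixteen scores.* Section 7b would allow about 16: TMT A and B; RAVLT learning and delayed recall; usual walk, rapid walk, chair rise, functional reach and static stands; physical and mental fatigability; five single scores. With assumed correlations of 0.5 to 0.7 within and 0.3 to 0.5 between instruments, the chance is 18 to 24% favouring the game and 36 to 46% in either direction.
- *Four tests*, one per labelled domain: 9.6% (ρ = 0) to 7.8% (ρ = 0.5) favouring the game.
- *Seven MRI volumes* as a separate family, either direction: 1 − 0.95^7 = 30.2% (ρ = 0), falling to 23.0% (ρ = 0.5).

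**6. Holm over nine, no true effects** (400,000 runs, ρ from 0 to 0.8): 4.9% down to 2.4% in either direction, and 2.5% down to 1.2% favouring the game.

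**7. Month-12 rules.** The case simulated has real month-3 effects on all nine outcomes that have vanished by month 12 (200,000 runs per cell, over a range of correlations and effect sizes). The largest chance of a false month-12 result was:

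- 37% if outcomes nominally significant at month 3 are each retested at 0.05;
- 8.8% if Holm is applied at month 12 only to the outcomes that passed Holm at month 3;
- 4.9% if Holm is applied to all nine at month 12 and durability is claimed only for outcomes that also passed at month 3.

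**8. Power with 33 per arm assumed, two-sample t-test.** The first Holm step is 0.05/9 = 0.0056.

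| Reading of the Stroop figures | d | Power at 0.05 | Power at 0.05/9 | n per arm, 80% at 0.05 | n per arm, 80% at 0.05/9 |
|---|---|---|---|---|---|
| Arm means, SD 0.33 | 0.485 | 49% | 19% | 68 | 114 |
| Standardised effects differing by 0.16 | 0.16 | 10% | 2% | 615 | 1,023 |

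**The case against.** The strongest reply is that no section says one favourable result is enough, so the 13 to 20% reflects an assumed rule. The only endpoint-specific planning concerns the Stroop; were it the lead, the figure would be 2.5%. It is true that the rule is assumed. But the plan does not declare the Stroop the lead, lists it as one of four cognitive tests, and offers no other success rule.

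Nine is also a count made by reading section 7b. Grouping by its four labelled domains gives fewer tests, but no domain composite is defined, and four tests would still give three to four times 2.5%.

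Some scores are close to defined: Pattern Comparison is timed over 30 seconds, and grip needs little more. Section 7d does name a Stroop metric, but it belongs to the cited study. The gap is widest for TMT, RAVLT and SPPB.

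Two further points stand and narrow the figures. The MRI list is open-ended and several software packages are named, so seven is a minimum. And section 7d speaks of pre-post benefit without naming a model or contrast, so the between-arm month-3 test is inferred from the objective.

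That this is a small academic trial does not remove the problem, since its stated aim is to determine efficacy.

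**Conclusion.** The concern holds. The efficacy objective has nine primary outcomes, a 5% test for each, and no decision rule. If any single favourable result is read as efficacy, the false-positive chance is about 13 to 20% for correlations of 0.5 to 0, and still about 8% at 0.8. That is roughly three to eight times the 2.5% of one test. The size depends on the assumed success rule and correlations; the missing rule does not. Without a rule, the primary conclusion is open to choice after the results are known, so this should be settled before any further comparative data are seen.

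**What to change.** Amend sections 7b and 7d before the n=22 look if it has not taken place. Otherwise date the change and state what had been seen.

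- **Primary analysis.** Between-arm comparison at month 3 in the ITT set, with per-protocol supportive and one defined score per instrument.
- **Option A.** Name one primary endpoint, tested at 0.05, and make the other clinical outcomes secondary. The Stroop is the natural candidate because the sample size cites it, but its score must be defined in the protocol.
- **Option B.** Keep the nine and apply Holm. Success is at least one Holm-significant result favouring the game. The team should accept openly that grip strength alone could then carry the claim, although the abstract's hypothesis concerns cognitive health.
- **MRI.** Close the list of volumes, fix the software, and treat them as a separate mechanistic family with Holm or FDR.
- **Month 12.** Label it supportive, or set a formal rule. Under A, test the primary endpoint at 0.05 only if it was significant at month 3. Under B, apply Holm across all nine at month 12 and claim durability only for outcomes also Holm-significant at month 3.

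The change is wording only, with three costs to disclose. A nominal p<0.05 on a demoted or unadjusted outcome no longer supports an efficacy claim. Power is low under either option and lower under B, which favours A. And Holm over all nine at month 12 is stricter than Holm over the selected outcomes, but the looser version does not always hold 5%.
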